## **Data collection and investigations**

- a. Eligible subjects will attend Infectious Diseases clinic at the Prince of Wales Hospital for assessment.

The first study visit will be scheduled before or within four weeks of initiation of ART. Annual visits will be scheduled thereafter for 5 years. During each study visit, demographic and clinical data will be collected. Physical examination will be performed. Blood and urine tests will be done at fasting state. Imaging, including ultrasonography of carotid arteries, DEXA scan and fibroscan, will be performed. Stool samples will be collected for microbiota study.

- b. Clinical data

A structured standardized research tool will be used to collect demographic and clinical data:

1. Age, gender, smoking status, alcohol consumption, exercise
2. Co-morbid illnesses, including history or new diagnoses of hepatitis B and C, diabetes, dyslipidemia, hypertension, metabolic syndrome, and cardiovascular diseases, as well as all comorbidities included in the Charlson comorbidity score
3. Date of HIV diagnosis, latest CD4 counts, latest HIV viral load
4. Medication history, including anti-retroviral drugs and other medications

- c. Physical examination and anthropometric measurements

1. Body weight and height, and body mass index
2. Hip and waist circumferences
3. Blood pressure
4. For subjects aged  $\geq 50$  years old, assessment of frailty, including hand grip strength, balance tests, 6-metre walking speed, will be performed
5. Neurocognitive assessment
  - i. International HIV dementia scale  
<https://www.hiv.uw.edu/page/mental-health-screening/ihds>
  - ii. Montreal Cognitive Assessment
  - iii. Symbol digit modality test (SDMT)
  - iv. Action fluency: ask the patient to say as many things that people do in 1 minute
  - v. Cogstate platform neurocognitive tests
  - vi. DASS 21 for screening of mood
  - vii. Lawton Instrumental Activities of Daily Living
6. Quality of life assessment
  - i. EQ-5D-5L questionnaire
7. Lung function test
  - i. FEV1 and FVC will be performed in smokers.

- d. Blood tests:

The following blood tests will be performed after an 8-hour fast:

1. Glucose, insulin, HbA1c
2. Total cholesterol, LDL cholesterol, HDL cholesterol, triglyceride, apolipoprotein A and apolipoprotein E
3. Complete blood count, creatinine, urate, calcium, phosphate, urea, ferritin

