  - i. Fractional tubular resorption of phosphate  $\{1- [(urine \text{ phosphate} \times \text{ serum Cr})/(urine Cr \times \text{ serum phosphate})]\} \times 100$  of  $<82\%$ ;
  - ii. Fractional excretion of uric acid  $\{[(urine \text{ uric acid} \times \text{ serum Cr})/(urine Cr \times \text{ serum uric acid})] \times 100\}$  of  $>15\%$ ;
  - iii.  $\beta 2\text{-microglobulin:creatinine} > 1000 \mu\text{g/g Cr}$ ; or
  - iv. RBP:creatinine  $>17\mu\text{g/mmol Cr}$

h. Osteopenia and osteoporosis

1. Osteoporosis is defined, according to World Health Organization criteria, as BMD T-score of  $\leq 2.5$  at the hip or spine in men  $\geq 50$  years old and post-menopausal women, or Z-score of  $\leq 2.0$  in men younger than 50 years old and pre-menopausal women.
2. Osteopenia is defined as a T-score between 1 and 2.49.

i. Chronic obstructive airway disease

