### **Electronic platform**

- a. An electronic database will be established for systematic collection of all the above clinical and laboratory data, and clinical outcomes.
- b. The collected data will be used to generate risk assessment for multiple HANA conditions. Clinical management will be recommended according to risk assessment.
- c. A report summarizing the risk assessment and diagnosis of each HANA condition will be generated for each patient after each study visit. The report will be submitted to their HIV physicians for further clinical management.

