### Statistical analysis

a. The incidence rate of each HANA defined as above will be calculated as:

$$\text{incidence rate of HANA (per 100 person - years)} \\ = \frac{\text{number of new diagnosis of HANA at end of follow up}}{\text{number of persons at risk * number of years of follow up}} \times 100$$

b. The incidence rate of each HANA will be determined for subjects started INSTI-based regimens and other non-INSTI-anti-retroviral regimens.

c. Variables, including demographic, clinical, treatment-related, and laboratory parameters, will be evaluated for association with development of various HANA, in univariate and multivariate analyses. Analyses will be performed for the whole cohort, and subgroup analyses will be performed in those initiated INSTI-based regimens and other non-INSTI-based regimens.

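### Osteopenia is set by T-score with no age limit while osteoporosis changes from Z- to T-score at age 50 (men) or menopause (women), so younger participants can fall in both classes or neither and a label can change with unchanged bone

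*Combined protocol and SAP*

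**What the plan says.** Outcome measures, item h.1 opens "Osteoporosis is defined, according to World Health Organization criteria, as BMD T-score of" 2.5 or beyond at the hip or spine; this applies to men aged 50 or over and post-menopausal women. A Z-score cut-off of 2.0 applies "in men younger than 50 years old and pre-menopausal women". Item h.2 then reads "Osteopenia is defined as a T-score between 1 and 2.49". It has no restriction by age, sex or menopausal status, and no clause excluding participants who already meet h.1. The cut-offs are printed without minus signs and are read as negative throughout this point.

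Under Data collection and investigations, "Annual visits will be scheduled thereafter for 5 years", and at each visit "Imaging, including ultrasonography of carotid arteries, DEXA scan and fibroscan, will be performed". The definitions feed two outputs. Under Statistical analysis, "The incidence rate of each HANA defined as above will be calculated as" new diagnoses over persons at risk times years of follow-up, and the rates are reported for INSTI and non-INSTI regimens. Under Electronic platform, "A report summarizing the risk assessment and diagnosis of each HANA condition will be generated for each patient after each study visit".

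The plan does not say which class takes precedence, or which scale applies once a participant passes from the younger to the older stratum.

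**The concern.** The two bone rules use different scales in the younger stratum, so they do not divide low bone density into ordered, separate classes. A younger participant may be counted under both conditions, or under neither despite a T-score below the osteopenia band. Worsening can even remove a label: with Z 0.7 above T, a move from T -2.4, Z -1.7 to T -2.6, Z -1.9 takes a man under 50 from osteopenia to no class.

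The scale also changes with age or menopause during follow-up, so osteoporosis status can alter between visits while the scores stay the same. A label gained this way enters the incidence numerator as a new diagnosis. At stake are the osteopenia and osteoporosis rates and the diagnoses in the per-visit reports.

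**Working it through.** The plan gives no planning figure for the bone outcomes, so there is none to reproduce. The check has three parts.

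**1. Logic, from item h with cut-offs read as negative**

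Younger stratum (men under 50, pre-menopausal women): osteoporosis if Z ≤ -2.0. Older stratum: osteoporosis if T ≤ -2.5. Either stratum: osteopenia if -2.49 ≤ T ≤ -1.

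| T, Z (unchanged) | Before the switch | After the switch |
|---|---|---|
| -2.3, -2.1 | osteoporosis and osteopenia | osteopenia only |
| -2.6, -1.9 | neither | osteoporosis |

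The younger rule Z ≤ -2.0 is the same as T ≤ -2.0 - d, where d = Z - T. It coincides with T ≤ -2.5 only at d = 0.5. Below 0.5 the switch can remove labels; above 0.5 it can create them.

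**2. Share of the younger stratum**

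Assumptions, none of them in the documents: Z is normal with SD 1 and mean m = 0 or -0.5, and T = Z - d. Φ is the standard normal distribution function.

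- Meets osteoporosis: Φ(-2 - m).
- Meets both: Φ(-2 - m) - Φ(-2.49 + d - m), if positive.
- Meets neither although T ≤ -2.5: Φ(-2.5 + d - m) - Φ(-2 - m), if positive.

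| m | d | Osteoporosis | Both | Neither |
|---|---|---|---|---|
| 0 | 0 | 2.3% | 0.0228 - 0.0064 = 1.6% | 0 |
| 0 | 0.2 | 2.3% | 0.0228 - 0.0110 = 1.2% | 0 |
| 0 | 0.5 | 2.3% | 0 | 0 |
| 0 | 0.7 | 2.3% | 0 | 0.0359 - 0.0228 = 1.3% |
| -0.5 | 0 | 6.7% | 0.0668 - 0.0233 = 4.4% | 0 |
| -0.5 | 0.2 | 6.7% | 0.0668 - 0.0367 = 3.0% | 0 |
| -0.5 | 0.5 | 6.7% | 0 | 0 |
| -0.5 | 0.7 | 6.7% | 0 | 0.0968 - 0.0668 = 3.0% |

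Among those meeting the younger osteoporosis rule, the share also meeting osteopenia is 72% (m = 0, d = 0), 52% (m = 0, d = 0.2) and 65% (m = -0.5, d = 0).

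**3. In people**

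The age mix is not given, so these counts are illustrations. If 300 of the 400 are in the younger stratum and m = -0.5, about 300 × 0.0668 = 20 meet osteoporosis. About 300 × 0.0435 = 13 of these also meet osteopenia at d = 0. At d = 0.7 none overlap, and about 300 × 0.0300 = 9 participants fall in neither class.

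If 40 to 80 participants change stratum in follow-up and d = 0.7, false incident osteoporosis cases number between 40 × 0.0132 = 0.5 and 80 × 0.0300 = 2.4.

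**The case against.** **Osteopenia may be meant only for the T-score stratum.** The value 2.49 plainly complements the T-score cut-off of 2.5, and h.1 introduces T-scores only for older men and post-menopausal women. That reading would remove the overlap, but the text does not state it. The plan writes an age limit where it wants one, as for frailty. The reading also leaves the change of scale untouched.

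**Overlap is not a defect in itself.** The overweight and obesity definitions are nested too. However, those share one scale, so a higher BMI never loses a class; the bone rules lack that property.

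**A label lost at the switch may not alter incidence.** This stands in part. Osteoporosis present at baseline was not at risk, osteoporosis diagnosed earlier in follow-up was already a new diagnosis, and the osteopenia is not new. The loss matters only if status is read at the last visit. The numerator's wording, which ties new diagnoses to the end of follow-up, leaves that open.

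**The numbers are small and assumed.** This stands. Overlap and gap need opposite values of Z - T and do not occur at the same gap.

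Three stronger readings may tempt a reader, and the documents do not support them:

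- That everyone aged 45-49 at entry changes scale. Age 50 applies to men only; women change at menopause, whatever their age.
- That osteopenia and osteoporosis cannot be told apart in younger participants generally. Few are affected, and stored scores can be reclassified.
- That the regimen comparison is shown to be biased. The switch follows age or menopause, not regimen. Regimens are chosen by physicians, so the age mix may differ between groups, but no imbalance is documented.

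**Conclusion.** The concern holds as a defect of definition with a small numerical effect. Applied as written, item h allows a younger participant to be in both bone classes or in neither. It also changes scale within follow-up for men aged 45-49 at entry and for women who reach menopause. The artefact that reaches incidence under any reading is the move from neither class to osteoporosis.

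Assuming Z is normal with SD 1 and mean 0 to -0.5, overlap is 1.6% to 4.4% of the younger stratum if T equals Z and zero once T is 0.5 or more below Z. The share in neither class is 1.3% to 3.0% if T is 0.7 below Z. These are alternatives and must not be added. Misclassification at the switch itself is likely to involve only a handful of participants. The mean, the Z-T gap and the age mix are not in the documents, so the true size cannot be fixed. The change is still worth making, because it costs little and the classification is otherwise undefined for these participants.

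**What to change.** In Outcome measures, item h, for the research incidence analysis only:

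- Assign each participant the T- or Z-score rule that applies at baseline, and keep it at all visits.
- Make the two classes mutually exclusive, with osteoporosis taking precedence, and leave no gap below the osteopenia band.
- State whether osteopenia is reported in the Z-score stratum. This is for the sponsor to decide. Restricting it to the T-score stratum would settle the overlap but remove that outcome for all men under 50 and all pre-menopausal women.

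In Statistical analysis, add percentage change in hip and spine BMD by regimen as a supporting analysis. It needs no cut-off and uses DEXA data already collected.

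The cost is revised outcome wording and one extra continuous analysis, with no new measurements. The downside is that the research label may differ from the clinical label after a participant crosses age 50 or menopause, so the plan should say that the per-visit reports are not governed by the research rule.

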1. FEV1/FVC  $<0.7$

j. Frailty and sarcopenia in those aged 50 and above

1. Frailty is defined by Frailty phenotype measurement, according to Fried definition

k. Sarcopenia is defined as appendicular lean mass (kg)/height(m^2)  $< 2$  standard deviations below the mean for young healthy adults (cut-offs were  $< 7.26 \text{ kg/m}^2$  for men and  $< 5.45 \text{ kg/m}^2$  for women)

[figure not shown]
l. Retinal vasculopathy

1. Presence of HIV retinopathy, retinal vein occlusions and retinal artery occlusions

### **Electronic platform**

- a. An electronic database will be established for systematic collection of all the above clinical and laboratory data, and clinical outcomes.
- b. The collected data will be used to generate risk assessment for multiple HANA conditions. Clinical management will be recommended according to risk assessment.
- c. A report summarizing the risk assessment and diagnosis of each HANA condition will be generated for each patient after each study visit. The report will be submitted to their HIV physicians for further clinical management.

### **Study Flowchart**

\*During each study visit, demographic and clinical data will be collected. Physical examination will be performed. Blood and urine tests will be done at fasting state. Imaging, including ultrasonography of carotid arteries, DEXA scan and fibroscan, will be performed. Stool samples will be collected for microbiota study.

### Sample size calculation

There were around 700 new HIV infections reported in Hong Kong in 2015 and 2016. Based on previous published data, the risk of developing metabolic syndrome is approximately 20% at 96 weeks after initiation of ART, a sample size of 400 will give a 95% confidence interval from 16% to 24% at 96 weeks. Using the same 400 patients, we would be able to detect with 95% confidence an odds ratio of 2 for any risk factors with respect to the incidence of metabolic syndrome assuming that the prevalence is 20% and we would like to have an estimate of the population odds ratio to within 50% of the true value (i.e. a lower bound of 1.0 for the 95% confidence interval of the odds ratio) even after adjusted for type I error due to multiple risk factors.

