### **Study design**

This is a prospective, longitudinal, cohort study. 400 newly diagnosed HIV-infected individuals attending HIV clinics in Hong Kong will be recruited. Clinical assessment, and laboratory and imaging studies will be performed at baseline prior to initiation of anti-retroviral regimen, than annually thereafter for 5 years. Choice of anti-retroviral regimen will be decided by the in-charge HIV physician. Incidence of development of various HANA conditions will be determined for those initiated INSTI-based regimens and other anti-retroviral regimens. An electronic platform will be used to formulate risk prediction for various clinical outcomes, and serve as a clinical decision support tool.

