#### **b. Inclusion criteria:**

1. Confirmed HIV infection by HIV antibody or RNA test
2. Age  $\geq 18$  years old
3. Anti-retroviral treatment naïve, within 6 months of initiation of anti-retroviral drugs, or switching ART regimens within 24 months
4. Agree to initiate anti-retroviral therapy (ART) as determined by in-charge HIV physician

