#### **c. Exclusion criteria:**

1. Pregnancy
2. Refusal to consent

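### The 16% to 24% interval for metabolic syndrome assumes that all 400 recruits are free of it at entry and evaluable at 96 weeks, so the stated precision is somewhat optimistic

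*Combined protocol and SAP*

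**What the plan says.** The Sample size calculation section starts from published data: "the risk of developing metabolic syndrome is approximately 20% at 96 weeks after initiation of ART". From this it concludes that "a sample size of 400 will give a 95% confidence interval from 16% to 24% at 96 weeks". It then carries the same 400 patients into a statement about detecting an odds ratio of 2 for risk factors "with respect to the incidence of metabolic syndrome assuming that the prevalence is 20" percent.

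The Study design section shows that 400 is the recruitment target: "400 newly diagnosed HIV-infected individuals attending HIV clinics in Hong Kong will be recruited".

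The inclusion criteria cover confirmed HIV infection, age 18 or over, agreement to start treatment, and treatment status, the last worded as "Anti-retroviral treatment naïve, within 6 months of initiation of anti-retroviral drugs, or switching ART regimens within 24 months". The exclusion criteria have two entries, pregnancy and "Refusal to consent". Neither list mentions metabolic syndrome. Under Data collection and investigations, a history of metabolic syndrome is recorded, so existing cases are foreseen.

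The Statistical analysis section (item a) defines each incidence rate with the number at risk, multiplied by years of follow-up, as the denominator. On follow-up, "Annual visits will be scheduled thereafter for 5 years". No section gives an expected loss rate, a baseline prevalence of metabolic syndrome, or an inflation of the sample size.

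**The concern.** A risk of developing a condition applies to people who do not yet have it. Someone who enters with metabolic syndrome cannot become a new case and drops out of the denominator that the Statistical analysis section defines. Someone lost before the two-year assessment contributes no outcome at that time. The published interval makes no deduction for either group.

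Existing cases are likely under these criteria. There is no upper age limit, people already on treatment may enter, and the Outcome measures section counts any three of five components, with treatment for a component also counting.

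At stake is the only precision the plan states for its incidence objective. It describes 400 condition-free, fully followed people, which is not the group the criteria recruit. The odds-ratio statement uses the same denominator.

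**Working it through.** **Inputs from the protocol.** Risk p = 0.20, n = 400 and 95% confidence (Sample size calculation); 400 recruited (Study design).

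**Inputs the protocol does not give.** Baseline prevalence of metabolic syndrome and loss by the two-year assessment. Both are assumptions here: 10% to 30% prevalent and 0% to 20% lost.

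**Step 1: reproduce the stated figure.** The Wald interval is p ± 1.96 × √(p(1 − p)/n). With p = 0.20 and n = 400, √(0.16/400) = 0.020 and 1.96 × 0.020 = 0.0392. The interval is 16.08% to 23.92%, which rounds to 16% to 24%. Other methods agree closely at n = 400: Wilson gives 16.4% to 24.2% and Clopper-Pearson 16.2% to 24.3%. The stated figure therefore uses all 400.

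**Step 2: the same formula for those at risk and evaluable.** n = 400 × (1 − prevalence) × (1 − loss), with p held at 0.20.

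| Prevalent at entry | Lost | n | Half-width (points) | 95% interval |
|---|---|---|---|---|
| 0% | 0% | 400 | 3.92 | 16.1% to 23.9% |
| 10% | 0% | 360 | 4.13 | 15.9% to 24.1% |
| 10% | 10% | 324 | 4.36 | 15.6% to 24.4% |
| 20% | 0% | 320 | 4.38 | 15.6% to 24.4% |
| 20% | 10% | 288 | 4.62 | 15.4% to 24.6% |
| 20% | 20% | 256 | 4.90 | 15.1% to 24.9% |
| 30% | 20% | 224 | 5.24 | 14.8% to 25.2% |

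Across the assumed range the half-width is 4.13/3.92 = 1.05 to 5.24/3.92 = 1.34 times the stated one, that is 5% to 34% wider.

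**Step 3: how much removal the stated figure tolerates.**
- Unrounded, a half-width of at most 4.0 points needs n ≥ 1.96² × 0.16/0.04² = 384.1, so 385 people. That leaves a margin of 15 out of 400, just under 4%.
- Rounded to whole percents, the interval reads 16% to 24% while the half-width is below 4.5 points. This needs n ≥ 1.96² × 0.16/0.045² = 303.5, so about 304 people, or 1 − 304/400 = 24% combined removal.

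The odds-ratio precision is not recalculated: the paragraph gives no separate exposure split, and its use of the word prevalence is ambiguous.

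**The case against.** The strongest reply is that nothing is miscalculated and little changes. That is largely right. The plan quotes whole percents, and several of the assumed scenarios (n = 360, 324 and 320) still round to 16% to 24%. At n = 288 each limit moves by 0.7 points, and at n = 224 by 1.3. No design choice is shown to turn on this. The size also rests entirely on assumed prevalence and loss, and the protocol does not say to which population the published 20% applies. What survives is the denominator: on the plan's own wording the quantity is new disease, existing cases can enrol, and no loss is allowed for.

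Reading 20% as a prevalence, as the odds-ratio sentence might suggest, does not remove the point. Loss would still apply, and the plan would then state no precision for incidence at all.

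A reader might infer more than the documents support:
- **That the risk-factor analyses lose events in proportion**, with 0.20 × 288 ≈ 58 or 0.20 × 224 ≈ 45 instead of 0.20 × 400 = 80. The plan states no event count. Follow-up runs for five years and the risk-factor analyses are not confined to 96 weeks, so two-year counts are not the events available to them.
- **That prevalence is simply the wrong word and should be replaced.** In an odds-ratio calculation it could mean the outcome risk or the frequency of the risk factor. Replacing it outright could corrupt the sentence.
- **That the absence of a week-96 visit is a fault.** The year-2 visit falls about 104 − 96 = 8 weeks later, and no effect on the interval has been shown.

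**Conclusion.** The point holds as a minor one about stated precision. The 16% to 24% interval is correct for 400 people at risk and evaluable, but the design recruits 400 people of whom an unstated number will be neither. With 10% to 30% prevalent and 0% to 20% lost, the half-width is wider by about 0.2 to 1.3 points. These ranges are assumptions, and p is held at 20% throughout, so the exact shortfall cannot be fixed from the documents. Nothing here shows that the study is too small for its purpose or that more patients are needed.

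**What to change.** Keep 400 enrolled and revise the Sample size calculation section in three places:

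1. Have the sponsor state its expected baseline prevalence of metabolic syndrome and its expected loss by the year-2 visit, then give the interval for the resulting at-risk evaluable number. For illustration only, about 290 people would give about 15% to 25%. The sponsor should supply its own inputs.
2. Base the odds-ratio statement on that same at-risk number rather than on all 400.
3. Have the sponsor clarify whether the 20% prevalence in the odds-ratio sentence means the outcome risk or the prevalence of the risk factor.

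The cost is a few sentences in one section, the odds-ratio statement reworked on the smaller number, and a slightly less favourable stated precision. No extra patients or procedures are needed.

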## **A prospective longitudinal cohort study to determine the incidence of HIV-associated non-AIDS conditions in newly diagnosed HIV-infected individuals initiating integrase inhibitor-based and other anti-retroviral regimens**

### **Background**

Integrase strand transfer inhibitor (INSTI) based-therapy is currently the recommended antiretroviral regimen in most guidelines. Efficacy in terms of virological suppression of INSTI-based regimens was either superior or non-inferior to other comparators in clinical trials performed in both treatment naïve and experienced individuals. Moreover, unlike other classes of anti-retroviral agents, transmitted drug resistance was uncommon even after years of introduction of INSTI on a population level, potentially allowing this class of drug to remain as recommended first-line treatment in the future.

Previous clinical trials comparing INSTIs and other anti-retroviral regimens in treatment-naïve individuals consistently showed lower discontinuation rates secondary to adverse reactions. For treatment-experienced individuals, switching from non-nucleotide reverse transcriptase inhibitor (NNRTI) or protease inhibitor (PI)-containing to an INSTI-containing regimen often resulted in better lipid profiles as well as tolerability and patient satisfaction. INSTIs have been shown to improve blood pressure control in those with underlying hypertension receiving anti-hypertensive treatment. INSTI also had lesser decline in bone loss when compared to protease inhibitors. On the other hand, integrase inhibitors have been reported to be the cause of metabolic complications, and neuropsychiatric adverse reactions. Transient drop in renal function and other renal complications in individuals taking some INSTIs had also been reported.

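### The claim that 400 patients detect an odds ratio of 2 for every risk factor after multiplicity adjustment fails for uncommon and very common factors, and the analysis section contains no adjustment

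*Combined protocol and SAP*

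**What the plan says.** The Sample size calculation makes two statements about 400 patients. The first is that a 20% risk of metabolic syndrome at 96 weeks would be estimated with a 95% confidence interval of 16% to 24%. The second is that "we would be able to detect with 95% confidence an odds ratio of 2 for any risk factors", "assuming that the prevalence is 20" per cent. The precision target is an estimate within 50% of the true odds ratio, spelled out as "a lower bound of 1.0 for the 95% confidence interval of the odds ratio", and it is said to be met "even after adjusted for type I error due to multiple risk factors". No share of patients with the factor, number of factors, adjustment method or power is given.

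Statistical analysis, item c, describes the corresponding analysis: "Variables, including demographic, clinical, treatment-related, and laboratory parameters, will be evaluated for association with development of various HANA", in univariate and multivariate models, for the whole cohort and by regimen group. It mentions no multiplicity adjustment and no number of factors. Item a counts incidence over "number of persons at risk * number of years of follow up", so patients who already have a condition at baseline are outside the denominator.

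**The concern.** The precision of an odds ratio depends on how patients divide between exposed and unexposed. A fixed total of 400 cannot give the same lower bound for a factor in 5% of patients as for one in 50%, and a multiplicity adjustment widens every interval further. The statement sets no limit on either.

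Evaluating risk factors for each condition is the second listed objective, and as written it reads as sized for any factor with type I error already allowed for. Two misreadings follow. A null result for a rare or near-universal factor could be taken as evidence against an odds ratio of 2. A positive result could be taken as multiplicity-adjusted.

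The upper end of the range also bears on the study's own regimen comparison. The Background says INSTI-based therapy "is currently the recommended antiretroviral regimen in most guidelines", and the Study design leaves the choice of regimen to the treating physician. The share on INSTI may therefore be high, although the protocol does not state it.

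**Working it through.** **Inputs.** From the Sample size calculation: n = 400, odds ratio (OR) 2, 20%, two-sided 95% interval, required lower bound 2 × 0.5 = 1.0. Not stated and therefore varied: the share f of patients with the factor, and the number of tests k. Bonferroni is assumed for the adjustment.

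**The plan's own interval.** 0.20 ± 1.96 × √(0.20 × 0.80/400) = 0.20 ± 0.039, or 16.1% to 23.9%. This agrees with the stated 16% to 24%.

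**Odds ratio, 20% risk in the unexposed.** The odds in the unexposed are 0.25, so OR 2 gives odds 0.5 and p1 = 0.333, with p0 = 0.20.

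- SE(ln OR) = √{1/[400·f·p1(1−p1)] + 1/[400·(1−f)·p0(1−p0)]}
- Lower bound = 2·exp(−z·SE), with z = 1.96 unadjusted and 2.576 for five tests
- Largest number of tests = 0.05 / {2[1 − Φ(ln 2/SE)]}, rounded down

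Example, f = 0.10: SE = √{1/(40 × 0.2222) + 1/(360 × 0.16)} = 0.360, and the lower bound is 2·exp(−1.96 × 0.360) = 0.99.

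| Share with factor | SE | Lower bound, unadjusted | Lower bound, five tests | Tests that fit |
|---|---|---|---|---|
| 5% | 0.491 | 0.76 | 0.56 | 0 |
| 10% | 0.360 | 0.99 | 0.79 | 0 |
| 20% | 0.275 | 1.17 | 0.98 | 4 |
| 30% | 0.245 | 1.24 | 1.07 | 10 |
| 50% | 0.232 | 1.27 | 1.10 | 17 |
| 70% | 0.261 | 1.20 | 1.02 | 6 |
| 80% | 0.304 | 1.10 | 0.92 | 2 |
| 90% | 0.411 | 0.89 | 0.69 | 0 |

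Solving for a lower bound of 1.0 gives these shares:

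- one test: 10.5% to 86.0%
- five tests: 21.4% to 72.5%
- ten tests: 28.8% to 64.0%
- 18 tests: 42.2% to 49.7%
- 19 or more: none

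The list headed "The following blood tests will be performed after an 8-hour fast" has more than 40 measures. How many would be tested is not stated. With 40 tests of binary factors the best lower bound at any share is 0.95.

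**Other readings of the 20%.**

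- *Whole-cohort risk* (p0 solved from f·p1 + (1−f)·p0 = 0.20): 10.9% to 78.4% unadjusted and 24.8% to 57.4% for five tests. Six tests fit at f = 50% and three at 20%; none fit anywhere from nine tests. The bound is 0.98 at both 10% and 80%.
- *Share of patients with the factor*: the bound is 1.17 and four tests fit, or three if whole-cohort risk is also 20%. This covers only that one prevalence.

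**Meaning of just meeting the criterion.** Power is Φ(ln 2/SE − 1.96), about 50% at the edge of each range. Unadjusted, with 20% risk in the unexposed, it is 85% at f = 50%, 71% at 20%, 49% at 10% and 39% at 90%.

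**Regimen comparison, assuming 90% on INSTI.** For OR 0.5 (the hypothesised direction) and 20% risk on non-INSTI, p1 = 0.111 and SE = √{1/(360 × 0.0988) + 1/(40 × 0.16)} = 0.429. The upper bound is 0.5·exp(1.96 × 0.429) = 1.16. In this direction the criterion fails above about 83.5% on INSTI. With 20% as whole-cohort risk the upper bound is 1.02.

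**Sensitivity, unadjusted, 20% risk in the unexposed unless varied.**

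- Later follow-up, assumed risk in the unexposed 25% to 45%: the range widens to about 9% up to 88%–91%. A 5% factor still misses, at 0.79 to 0.81.
- Assumed 10% prevalent at baseline and 10% lost (n = 0.9 × 0.9 × 400 = 324): 13.5% to 82.2%.
- Assumed 20% and 20% (n = 0.8 × 0.8 × 400 = 256): 18.5% to 76.1%.

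The formula is for one binary factor without covariates. Correlated covariates in the multivariate models would usually widen the interval.

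**The case against.** The strongest reply is that nothing has been miscalculated. The incidence interval reproduces. At an even split the criterion needs only 86 per group (172 in all) without adjustment, and 400 suffices for up to 17 Bonferroni tests. On this view the text is underspecified, not wrong. This stands as a defence of 400, but not of the sentence, which asserts a property for any factor and after adjustment that the design lacks on every reading of the 20%.

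Second, the 20% is introduced as a cohort risk, so placing it in the unexposed is not the most natural reading. That is a fair point. It is why both are reported, and the cohort reading gives the narrower ranges. If the 20% is the share with the factor, the statement holds, but only at that prevalence and for three or four tests.

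Third, the 90% INSTI share is an assumption, and the sentence does not claim to size the regimen comparison. Both are correct. The 1.16 also depends on the risk assumed, and on the whole-cohort reading it is a near miss at 1.02. The figures are illustrative.

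Fourth, many laboratory measures are continuous. Taking OR 2 per standard deviation, SE is roughly 1/√(400 × 0.16) = 0.125 and the lower bound 2·exp(−1.96 × 0.125) = 1.57, comfortably above 1. That stands. The protocol gives no unit for continuous factors, so the ranges here apply to binary ones. The 18-test ceiling likewise belongs to 20% risk in the unexposed; at an assumed 45%, 40 tests would fit for factors in about 35% to 67% of patients.

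**Conclusion.** The concern holds. On the plan's own criterion, OR 2 is not detectable for any risk factor with 400 patients. The unadjusted range is about 10.5% to 86% of patients with the factor if 20% is risk in the unexposed, and 10.9% to 78.4% if it is whole-cohort risk. The miss at 10% is narrow; those at 5% and 90% are not. The adjustment claim cannot be checked, because neither method nor number of factors is given, and the analysis section does not carry it out. With five Bonferroni tests the ranges fall to 21.4%–72.5% and 24.8%–57.4%.

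These figures assume binary factors, no covariates, and all 400 at risk and followed to 96 weeks. Prevalent cases and losses narrow them; higher risk at later visits widens them somewhat. The sample size and the incidence precision are not in question. The statement should be corrected, and confidence in that is high.

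**What to change.** Keep 400 and make four changes.

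1. State whether the 20% is risk in the unexposed, risk in the whole cohort, or the share of patients with the factor.
2. Replace the claim about any factor with the range of factor prevalence, at both ends, and the number of tests for which the lower bound is at least 1.0. If 20% is risk in the unexposed: a binary factor present in about 11% to 86% of patients without adjustment, or 22% to 72% with Bonferroni for five factors. If it is whole-cohort risk: 11% to 78%, or 25% to 57%.
3. Say that these figures assume all 400 are at risk and followed to 96 weeks, and worsen with baseline cases or losses.
4. Make the Sample size calculation and Statistical analysis sections agree. Either item c states the adjustment and the number of prespecified factors, or the adjustment claim is deleted and the risk-factor analyses are labelled exploratory.

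Optionally, add the minimum detectable odds ratios at 80% power (n = 400, unadjusted, 20% risk in the unexposed): 1.9, 2.0, 2.15 and 2.7 at 50%, 30%, 20% and 10% exposed, and 2.3 and 3.15 at 80% and 90%.

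The cost is rewording and less favourable stated figures, with no extra patients. If the adjustment is kept, the factors must be prespecified.
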